1.1.3 Clinical Safety

The safety and preliminary efficacy of patritumab deruxtecan were evaluated in the on-going Phase I/II Study U31402-A-J101 in US and Japan in patients with metastatic breast cancer (MBC). The trial enrolled advanced/unresectable MBC patients (irrespective of subtype) with HER3 positive tumors who were refractory/intolerant to standard therapy in the dose escalation

CONFIDENTIAL

phase. Patients with HER3-positive MBC who had received ≥ 2 and ≤ 6 prior chemotherapy regimens were then enrolled in the dose-finding phase and subsequent expansion phase. The expansion phase included HR+/HER2- and triple negative MBC patients with HER3 high expression and HR+/HER2- MBC patients with HER3 low expression. Two different doses of patritumab deruxtecan, 4.8 mg/kg and 6.4 mg/kg, were evaluated.

As of the data cut-off date of 05 August 2019, 144 of 145 patients enrolled in Study U31402-A-J101 had received patritumab deruxtecan: 34 patients in the dose escalation part, 32 patients in the dose-finding part, and 78 patients in the dose expansion part. A total of 141 (97.9%) patients had experienced at least 1 treatment-emergent adverse event (TEAE) and 138 (95.8%) patients had experienced at least 1 TEAE considered related to study drug by the Investigator. The most frequent TEAEs (in $>20\%$ of patients), all grades, regardless of causality and noted in descending order of frequency, included nausea (113 [78.5%] patients), decreased appetite (74 [51.4%] patients), platelet count decreased (65 [45.1%] patients), neutrophil count decreased (61 [42.4%] patients), vomiting (57 [39.6%] patients), white blood cell count decreased (53 [36.8%] patients), anemia (52 [36.1%] patients), diarrhea (50 [34.7%] patients), aspartate aminotransferase (AST) increased (41 [28.5%] patients), fatigue (40 [27.8%] patients), alanine aminotransferase (ALT) increased (36 [25.0%] patients), stomatitis (36 [25.0%] patients), constipation (32 [22.2%] patients), and alopecia and malaise (31 [21.5%] patients each).

There were 92 (63.9%) patients with TEAEs of Grade 3 or higher, including most commonly (in $>5\%$ of patients), neutrophil count decreased (37 [25.7%] patients), platelet count decreased (32 [22.2%] patients), anemia (25 [17.4%] patients), white blood cell count decreased (21 [14.6%] patients), thrombocytopenia (12 [8.3%] patients), neutropenia (11 [7.6%] patients), hypokalemia (10 [6.9%] patients), and AST increased (8 [5.6%] patients).

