6.1 Dose Modifications Due to Hematologic Toxicity

Dose reductions or holds and initiation of supportive care are allowed as clinically indicated by the treating physician. Patients whose treatment is delayed due to toxicity will discontinue study drug or will proceed with treatment when toxicity has improved (as long as the toxicity resolves within 126 days from the time of the last administration of patritumab deruxtecan) according to the dose modifications below.

Table 3 Dose Modifications Due to Hematologic Toxicities

	Worst Toxicity NCI CTCAE Version 5.0 Grade (unless otherwise specified)	Schedule Modification for patritumab deruxtecan
Blood and lymphatic system disorders		
Neutrophil count decreased	Grade 3 (500 - <1000/mm ³ ; 0.5-1 × 10 ⁹ /L)	Delay dose until resolved to ≤Grade 2, then resume patritumab deruxtecan.
	Grade 4 (<500/mm ³ ; <0.5 × 10 ⁹ /L)	Delay dose until resolved to ≤Grade 2, study treatment may be resumed after discussion and agreement between the Investigator and Medical Monitor. If treatment is resumed, then reduce by at least 1 dose level.
Febrile neutropenia (ANC <1000/mm³; <1 × 10⁹/L, fever >38.3°C or a sustained temperature of ≥38°C for more than 1 hour)	Grade 3 and 4	Delay dose until resolved, then reduce patritumab deruxtecan by 1 dose level and resume. Administration of G-CSF as prophylaxis for all subsequent cycles is recommended.

CONFIDENTIAL

	Worst Toxicity NCI CTCAE Version 5.0 Grade (unless otherwise specified)	Schedule Modification for patritumab deruxtecan
Anemia	Grade 3 (Hgb <8.0 g/dL)	Delay dose until resolved to \leq Grade 2 or baseline, then resume patritumab deruxtecan. For recurrent anemia, delay dose until resolved \leq Grade 2 or baseline, then reduce patritumab deruxtecan dose by 1 level. Consider transfusion according to institutional guidelines.
	Grade 4 (Life-threatening consequences; urgent intervention indicated)	Delay dose until resolved to \leq Grade 2 or baseline, then reduce patritumab deruxtecan dose by 1 level. Consider transfusion according to institutional guidelines.
Platelet count decreased	Grade 3 ($<50 - 25 \times 10^9/L$)	Delay dose until resolved to \leq Grade 1, then: 
 • If resolved in ≤ 14 days, resume patritumab deruxtecan. • If resolved in >14 days, patritumab deruxtecan may be resumed. Consider reducing patritumab deruxtecan by 1 dose level. Consider transfusion according to institutional guidelines.

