	Grade 4 ($<25 \times 10^9/L$)	Delay dose until resolved to \leq Grade 1, then reduce patritumab deruxtecan by 1 dose level. Consider transfusion according to institutional guidelines.
Lymphocyte Count Decreased	Grade 4 ($<0.2 \times 10^9/L$)	Delay dose until resolved to \leq Grade 2, then: 
 • If resolved in ≤ 14 days, resume patritumab deruxtecan. • If resolved in >14 days, then reduce patritumab deruxtecan by 1 dose level.

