Vomiting	Grade 3 (Tube feeding, TPN, or hospitalization indicated)	Delay patritumab deruxtecan until resolved \leq Grade 1, and consider treatment with antiemetics and / or corticosteroids as per Investigator's judgement and local practice/guidelines, then: 
 • If resolved to \leq Grade 1 in ≤ 7 days, resume patritumab deruxtecan. • If resolved to \leq Grade 1 in > 7 days, then reduce patritumab deruxtecan by 1 dose level.
	Grade ≥ 4	Discontinue patient from patritumab deruxtecan.
Premedicate with a two or three drug combination regimen (e.g., dexamethasone with either a 5-HT3 receptor antagonist or an NK-1 receptor antagonist as well as other drugs as indicated) for prevention of chemotherapy-induced nausea and vomiting (CINV).		
Diarrhea/Colitis	Grade 3	Delay patritumab deruxtecan until resolved \leq Grade 1, and consider treatment per local practice/guidelines, then: 
 • If resolved to \leq Grade 1 in ≤ 7 days, resume patritumab deruxtecan. • If resolved to \leq Grade 1 in > 7 days, then reduce patritumab deruxtecan by 1 dose level.
	Grade 4 (Life-threatening consequences; urgent intervention indicated)	Discontinue patient from patritumab deruxtecan.
Mucositis oral	Grade 3	Delay patritumab deruxtecan until resolved \leq Grade 1, and consider treatment per local practice/guidelines, then: 
 • If resolved to \leq Grade 1 in ≤ 14 days, resume patritumab deruxtecan. • If resolved to \leq Grade 1 in > 14 days, then reduce patritumab deruxtecan by 1 dose level.

CONFIDENTIAL

	Worst Toxicity NCI CTCAE Version 5.0 Grade (unless otherwise specified)	Schedule Modification for Patritumab deruxtecan
	Grade 4 (Life-threatening consequences; urgent intervention indicated)	Discontinue patient from patritumab deruxtecan.
Other adverse events (Non-laboratory or Laboratory)	Grade 3	Delay patritumab deruxtecan until resolved \leq Grade 1, or baseline, then: 
 • If resolved in ≤ 7 days, resume patritumab deruxtecan. • If resolved to in > 7 days, then reduce patritumab deruxtecan by 1 dose level.
	Grade 4 (Life-threatening consequences; urgent intervention indicated)	Discontinue patient from patritumab deruxtecan.

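### Table 3 has no rule for white cell decrease or Grade 3 lymphocyte decrease, and the two texts that could apply instead conflict with Table 3 and with each other

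*Combined protocol and SAP*

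**What the plan says.** Three parts of the protocol bear on a low blood count.

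- **Section 6 (general rule).** For any toxicity of Grade 3 or higher, treatment waits for recovery to Grade 1 or better, or to baseline where baseline was above Grade 1. It then restarts one dose level down, where medically appropriate. Reductions are permanent. Blood counts are not excepted.
- **Section 6.1, "Table 3 Dose Modifications Due to Hematologic Toxicities".** For Grade 3 neutrophils: "Delay dose until resolved to ≤Grade 2, then resume patritumab deruxtecan". Grade 4 neutrophils are also held to Grade 2 or better and may resume by agreement with the Medical Monitor: "If treatment is resumed, then reduce by at least 1 dose level". The row "Lymphocyte Count Decreased" lists Grade 4 only. It is held to Grade 2 or better and resumed if that takes 14 days or less; otherwise "If resolved in >14 days, then reduce patritumab deruxtecan by 1 dose level". There is no row for white blood cell count decreased.
- **Section 6.2, Table 4.** The title limits the table to non-hematologic toxicities, but its last row is labelled "Other adverse events (Non-laboratory or Laboratory". At Grade 3 the dose is held to Grade 1 or better, or baseline, and resumed if this takes 7 days or less; otherwise "If resolved to in > 7 days, then reduce patritumab deruxtecan by 1 dose level". At Grade 4, described as life-threatening, the patient is discontinued.

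No sentence says which of these governs a blood count that Table 3 leaves out.

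The omission is not of a rare event. Section 1.2 names white cell decrease among the identified risks, and Section 1.1.3 lists, among events of Grade 3 or higher, "white blood cell count decreased (21 [14.6%] patients").

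**The concern.** White cells, neutrophils and lymphocytes are all reported from one hematology sample (Schedule of Assessments, footnote i). If one of them has its own rule and another falls to a default with a different recovery target and a different trigger for reduction, a single sample can give a site two instructions. Two sites could then follow the protocol and dose the same patient differently.

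A reduction cannot be reversed, and Table 2 has only two levels below the starting dose. Section 10.4.3 also plans a summary of adverse events leading to discontinuation, so inconsistent handling would add noise to a reported safety result.

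**Working it through.** **Step 1: set the rules side by side.**

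| Event | Text | Recovery needed | Dose on restart |
|---|---|---|---|
| Neutrophils, Grade 3 | Table 3 | Grade 2 or better | Resume, no reduction |
| Neutrophils, Grade 4 | Table 3 | Grade 2 or better | If resumed, at least one level lower |
| Lymphocytes, Grade 4 | Table 3 | Grade 2 or better | Resume if 14 days or less; one level lower if more |
| Unlisted count, Grade 3 | Section 6 | Grade 1 or better, or baseline if above Grade 1 | One level lower, where medically appropriate |
| Unlisted count, Grade 3 | Table 4 last row | Grade 1 or better, or baseline | Resume if 7 days or less; one level lower if more |
| Unlisted count, Grade 4 | Section 6 | Grade 1 or better, or baseline if above Grade 1 | One level lower, where medically appropriate |
| Unlisted count, Grade 4 (life-threatening) | Table 4 last row | n/a | Discontinue |

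**Step 2: compare.**

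(a) *Lymphocytes, Grade 3 against Grade 4.* Suppose recovery takes more than 7 but not more than 14 days. The Grade 4 patient resumes without reduction on reaching Grade 2. The Grade 3 patient must reach Grade 1, or baseline if that was worse, and is then one level lower under Table 4, or under Section 6 where restart is medically appropriate. The milder grade has the stricter target and the earlier or default reduction. This lies within one adverse event term and holds under both routes. The exception on recovery target is a patient whose baseline was already above Grade 1.

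(b) *White cells against neutrophils, both Grade 3, one sample.* Neutrophils: Grade 2, resume, no reduction. White cells: Grade 1 or baseline, with reduction after 7 days (Table 4) or by default (Section 6).

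(c) *The two routes against each other.* For a Grade 3 event that recovers within 7 days, Table 4 says resume and Section 6 says one level lower. Beyond 7 days they agree on one level lower. An isolated white cell event is therefore ambiguous even with no neutrophil event beside it.

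**Step 3: how often.** Inputs: 21 of 144 treated patients in the earlier study (Section 1.1.3) and up to 121 planned patients (Synopsis; 60 + 40 + 21 = 121).

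- Plan's own figure: 21/144 = 0.1458, or 14.6%. It reproduces.
- Exact (Clopper-Pearson) 95% interval: 9.3% to 21.4%.
- Expected number in this study: 121 × 0.1458 = 17.6.
- Range: 121 × 0.0926 = 11.2 to 121 × 0.2142 = 25.9, so about 11 to 26 patients.

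This counts patients with a Grade 3 or higher white cell decrease and no Table 3 rule. The documents do not give the split between Grades 3 and 4, the overlap with neutrophil events, or any lymphocyte rate.

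**The case against.** The case for leaving the text alone has four parts.

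- *Table 4 is non-hematologic by title, and Sections 6.1 and 6.2 divide the two kinds of toxicity.* On that structure, laboratory events in its last row would mean non-hematologic ones. This is a fair reading, perhaps the more natural one. It removes Table 4 but not the problem: Section 6 then applies, and conflicts (a) and (b) remain.
- *Section 6 is a general rule that the tables displace.* It does differ from several listed rows, and its wording leaves room for judgement. But where the table has no row there is nothing to displace it.
- *Listing lymphocytes at Grade 4 only may mean that Grade 3 needs no action.* A site could read it so. The Section 6 sentence on Grade 3 or higher contradicts that reading, so it adds another possible instruction.
- *Other provisions could settle it.* Section 6 bases adjustments on the organ system with the greatest toxicity, which does not rank two counts in the same system. Section 6.1 lets the treating physician hold or reduce as clinically indicated, but does not say which recovery target governs.

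A reader might also infer that a Grade 4 white cell count forces permanent discontinuation while a Grade 4 neutrophil count on the same sample allows resumption. The documents do not support stating this as the rule. It arises only if Table 4 is read to cover blood counts, and that row's Grade 4 entry is qualified by life-threatening consequences, which a laboratory value alone may not meet.

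**Conclusion.** The point stands as a contradiction between stated dosing rules for two unlisted events. It rests most firmly on the lymphocyte inversion and on the disagreement between the two routes at Grade 3 with recovery within 7 days. Neither depends on two counts being low at once.

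If the earlier rate carried over, about 11 to 26 of 121 patients would have a Grade 3 or higher white cell decrease for which Table 3 has no rule. That is an assumption: the earlier study pooled several doses and schedules, while this one starts every patient at a single dose. A reader might infer that all of these patients would meet two conflicting rules on one sample. That does not follow, because a white cell and neutrophil conflict also needs a qualifying neutrophil event and the overlap is not reported. Nor do the documents allow any effect on response rate or PFS-6 to be sized.

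**What to change.** Reconcile Section 6, Table 3 and the last row of Table 4 for white blood cell count decreased and for Grade 3 lymphocyte decrease. Add one sentence stating which text governs hematologic laboratory events that Table 3 does not list, including whether Table 4 can apply to a blood count at all. The thresholds, timings and dose consequences are for the sponsor's clinical team, and no view is taken here on which rule is right.

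The cost is a wording change in a protocol amendment. It needs no new data, visits or analyses.

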6.2.1 Specific Recommendations for ILD

If a patient develops radiographic changes potentially consistent with ILD or develops an acute onset of new or worsening pulmonary or other related signs/symptoms, such as dyspnea, cough, or fever, rule out ILD.

If ILD is suspected, delay patritumab deruxtecan dosing pending further evaluation and start corticosteroid treatment promptly unless clinically contraindicated.

Evaluation must include CT (preferably high-resolution CT) and pulmonologist consultation (when the Investigator is not a pulmonologist). The following evaluations should also be obtained, as indicated:

- Infectious disease consultation as clinically indicated
- Blood cultures and CBC (other blood tests could be considered as needed)
- Bronchoscopy and bronchoalveolar lavage if clinically indicated and feasible
- Pulmonary function tests
- Pulse oximetry (peripheral capillary oxygen saturation [SpO₂])
- Arterial blood gases, as clinically indicated
- Diffusing capacity for carbon monoxide (DLCO), as clinically indicated
- One blood sample collection for PK analysis as soon as ILD is suspected, if feasible
- Other tests, as clinically indicated

If the AE is confirmed to be ILD, follow the management guidance outlined in Table 4. If a non-inflammatory/infectious etiology is confirmed by the Investigator, treat accordingly and resumption of patritumab deruxtecan may occur after discussion between the Investigator and Sponsor.

CONFIDENTIAL

All events of ILD regardless of severity or seriousness will be followed until resolution, including after drug discontinuation.

6.2.2 Specific Recommendations for Liver Function Test Abnormalities

For patients with Grade 3 liver enzyme elevations (AST/ALT), patritumab deruxtecan should be held until the values recover to \leq Grade 1. Patients with an elevation of ALT/AST $\geq 3 \times$ ULN in conjunction with a bilirubin $\geq 2 \times$ ULN may remain in the study if a correctable, non-drug-related cause of the liver test evaluations can be documented; otherwise, the patient must be discontinued from the study.

7. STUDY ASSESSMENTS AND EVALUATIONS

7.1 Overview

All patients should visit the study center on the days specified within this protocol. The complete Schedule of Assessments (SOA) for this study is presented at the beginning of this protocol. The key procedures required in this study include:

- Reporting of all AEs occurring after the first dose of study treatment
- Pre-treatment and on-treatment blood biomarker assessments
- Tumor biopsy biomarker assessments
- Tumor assessments (based on CT/positron emission tomography [PET]/ and/or magnetic resonance imaging [MRI] scan) according to RECIST v 1.1 (see Appendix B).

A cycle of treatment is scheduled to last 3 weeks (21 calendar days). Multiple procedures may be scheduled at the same time point relative to patritumab deruxtecan dosing. Vital signs and ECG assessments should be performed prior to specimen collections.

7.2 Screening

At enrollment, each potential research subject will provide written informed consent ≤ 28 days prior to initiation of treatment and prior to starting any study-specific procedures. Upon signature of the ICF, patients will be assigned a unique patient number as enrollment (screening) occurs.

The screening assessments described in the SOA will be collected, reviewed, and determined to be acceptable by the site Principal Investigator or designee after obtaining informed consent prior to the initiation of treatment.

The following screening assessments should be performed and recorded ≤ 28 days prior to initiation of treatment:

- Ophthalmologic exam
- 12-lead ECG triplicate
- CT scan of chest, abdomen, and pelvis
- Bone scan if bone metastasis is suspected

Ophthalmologic exams include a visual acuity test (early treatment diabetic retinopathy study [ETDRS] or Snellens), slit lamp examination, fundoscopy, and tonometry. Assessments may be

CONFIDENTIAL

repeated as clinically indicated as part of a scheduled or unscheduled visit. A 40 (+7) day FU assessment is required if an on-treatment assessment was abnormal at the time of discontinuation of study therapy, to confirm reversibility of the abnormality.

The following screening assessments should be recorded ≤ 7 days prior to initiation of treatment:

- Medical history and demographics
- Physical examination (including height and weight)
- ECOG performance status
- Vital signs
- Hematology including red blood cell (RBC) count, hemoglobin (Hb), hematocrit, reticulocytes, total white blood cell (WBC) count, absolute neutrophil count (ANC), absolute lymphocyte count, 5-part differential (neutrophils, lymphocytes, monocytes, basophils, eosinophils), and platelet count
- Biochemistry (sodium, potassium, phosphate, chloride, creatinine, calcium, venous bicarbonate HCO_3 or CO_2 , albumin, total protein, AST, ALT, alkaline phosphatase [ALP], bilirubin, lactate dehydrogenase, serum glucose, creatinine kinase [CK: if CK is elevated, then CK-MB, troponin I, and myoglobin should be reactively tested, with further follow-up as clinically warranted], serum urea nitrogen, and serum uric acid)
- Coagulation test - aPTT/PTT and INR/PT
- Urinalysis
- Screening pregnancy test (blood)

If these assessments are performed within 72 hours of initiation of treatment, they do not need to be repeated on Cycle 1 Day 1, with the exception of the ECOG performance status, an abbreviated physical examination, vital signs, and triplicate ECGs.

Concomitant medications present at study entry and/or during screening that are relevant to the patient's safety during the study as judged by the Investigator will be recorded in the electronic case report form (eCRF) (see Section 5.3 for details on concomitant medications).

7.3 Assessments During Study Treatment

Patients will remain on treatment as long as, in the opinion of the Investigator, they are deriving benefit and the criteria listed in Section 3.3 Discontinuation from Study Treatment are not met. Please refer to the SOA for detailed outlines of each visit during the treatment period for each part of the study.

7.3.1 Response Assessments

Patients will be re-evaluated for response to treatment every 2 cycles (6 weeks ± 5 days) for the first 6 months, and every 3 cycles (9 weeks ± 5 days) thereafter. Patients with PD or unacceptable toxicity should be discontinued from the study. Patients who are receiving clinical benefit in the opinion of the treating Investigator may be allowed to stay on study after consultation with the Medical Monitor. Patients with SD or response to therapy will continue treatment. The assessments to be performed at this time are specified in the SOA. Please refer

CONFIDENTIAL

to Appendix B Response Evaluation Criteria in Solid Tumors (RECIST) Version 1.1 for further instructions on evaluating response (e.g., PD, SD).

The following assessments will be performed if abnormal at baseline or if clinically indicated:

- CT scan of chest, abdomen, and pelvis
- CT scan head/MRI brain if history of central nervous system metastases

7.4 Follow-Up Periods and Study Completion

7.4.1 End-of-Treatment Visit

The end-of-treatment (EOT) visit will be performed as soon as possible (preferably within 7 days but no later than 14 days) after the Investigator decided with the patient to permanently discontinue the study treatment or when the Investigator became aware that the study treatment, had been discontinued.

If the patient discontinues treatment without having PD, tumor assessment/imaging should continue to be performed as outlined in the protocol until progression.

7.4.2 Forty-Day Safety Follow-Up

All patients will be followed after discontinuing study treatment until all treatment-related toxicity resolves or for at least 40 days (+7 days) post-study drug discontinuation or until the start of another anti-cancer treatment. Any concomitant medications received up to 30 days after the last dose of study medication should be recorded.

7.4.3 Progression-free Survival Follow-Up

If the patient discontinues treatment without having PD, tumor assessment/imaging should continue to be performed per standard of care until progression, withdrawal of consent, subsequent treatment, or the study is stopped. Follow-up for progression may be done by review of medical records every 3 months to confirm patient status.

